6.4.5.5. Renal Function Effects

Effects on renal function will be assessed through analysis of elevated creatinine.

The CTCAE will be applied for laboratory tests related to renal effects ([Table JPDA.6.6](#)). This CTCAE grading scheme is consistent with both Version 3.0 and Version 4.03 of the CTCAE guidelines.

Shift tables will show the number and percentage of subjects from baseline to maximum during the Dosing Period, with baseline depicted by highest grade during the baseline period. A shift table summary displaying the number and percentage of subjects with maximum postbaseline results will be presented by treatment group within the following categories:

- Decreased; postbaseline category < baseline category
- Increased; postbaseline category > baseline category
- Same; postbaseline category = baseline category.

Treatment-emergent lab abnormalities related to elevated creatinine occurring at any time during the Dosing Period will be tabulated using the CTCAE grades shown in [Table JPDA.6.6](#). Planned and unplanned measurements will be included.

Treatment-emergence will be characterized using 5 criteria:

- any increase in postbaseline CTCAE grade from worst baseline grade
- increase to Grade 1 or above at worst postbaseline
- increase to Grade 2 or above at worst postbaseline
- increase to Grade 3 or above at worst postbaseline
- increase to Grade 4 at worst postbaseline.

Table JPDA.6.6. Common Terminology Criteria for Adverse Events (CTCAE) Related to Renal Effects

Lab Test	CTCAE Version	Grade	Criteria in SI or CN Units
Elevated creatinine	3.0	0 (normal)	\leq ULN
		1	$>$ ULN and $\leq 1.5 \times$ ULN
		2	$> 1.5 \times$ ULN and $\leq 3 \times$ ULN
		3	$> 3 \times$ ULN and $\leq 6 \times$ ULN
		4	$> 6 \times$ ULN

Abbreviations: CN = conventional (US); CTCAE = Common Terminology Criteria for Adverse Events; SI = Système International; ULN = upper limit of normal.

6.4.5.6. Infections, Including Potential Opportunistic Infections

Infections will be defined using the PTs from the MedDRA Infections and Infestations SOC, with additional terms from the Investigations SOC being used in selected instances, as described below.

Treatment-emergent infections will be analyzed according to various groups of infectious events including:

- all infections
 - all PTs in the Infections and Infestations SOC,
- serious infections
 - all PTs in the Infections and Infestations SOC that are SAEs,
- infections that require therapeutic intervention (antibiotics, antivirals, antifungals, and so on)
 - all PTs in the Infections and Infestations SOC for which there is an antimicrobial concomitant medication associated with that event for that subject,
- herpes zoster
 - specific Lilly-defined PTs from the Herpes Viral Infections high-level term (HLT) in the Infections and Infestations SOC, shown in [Appendix 4](#),
- tuberculosis
 - specific Lilly-defined PTs from the Tuberculous Infections HLT and the Investigations SOC, shown in [Appendix 5](#)
- viral hepatitis
 - all PTs from the Hepatitis Viral Infections HLT (HLT code 10057212) in the Infections and Infestations SOC.

For each infection event, the frequency for each PT will be provided, ordered by decreasing frequency in the LY3337641 highest dose group by infection group: all infections, serious infections (overall and on each approach to identifying SAEs), infections that require therapeutic intervention, herpes zoster infections, tuberculosis, and viral hepatitis.

In addition to the incidence of infectious AEs by MedDRA PT as described above, the number and percentage of subjects with treatment-emergent infectious AEs by treatment group will be summarized and listed.

Potential Opportunistic Infections:

Potential opportunistic infections (POIs) will be identified according to 2 different approaches.

POIs are identified from TEAEs based on a Lilly-defined list of MedDRA PTs, shown in the [Appendix 6](#). These PTs are a subset of terms from the Infections and Infestations SOC.

For the POIs identified from MedDRA PTs, the number and percentage of subjects overall and for each specific PT will be summarized by treatment group, with specific event terms ordered by decreasing frequency in the LY3337641 highest dose.

Association of Infections with Lymphopenia or Neutropenia:

The relationship between the occurrence of lymphopenia and neutropenia with the occurrence of infections will be evaluated based on case reviews. Inferential analyses and/or graphical displays may be conducted if warranted. Infection outcomes considered for this analysis are any infection, any serious infection, infections that require therapeutic intervention (antibiotics, antivirals, antifungals, and so on), tuberculosis, herpes zoster, and viral hepatitis.

6.4.5.7. Allergic Reactions/Hypersensitivities

Allergic reactions/hypersensitivities will be examined within the context of anaphylactic reactions. Subjects with a treatment-emergent anaphylactic reaction will be identified using the MedDRA Anaphylactic Reaction SMQ (SMQ 20000021). This SMQ is unique compared to most SMQs in that an algorithmic approach is taken to identify events.

Anaphylaxis has been broadly defined as “a serious allergic reaction that is rapid in onset and may cause death” (Sampson et al. 2006). Sampson and colleagues described a two-tiered approach to identify cases of anaphylactic reaction, an approach which is mimicked by the algorithmic approach taken for the Anaphylactic Reaction SMQ.

The algorithm is defined in the following manner within the Introductory Guide for Standardized MedDRA Queries (SMQs) version 17.0: “All narrow search terms as well as: if one term from Category B and one term from Category C is present, or if one term from (Category B or Category C) plus one term from Category D.” This algorithm is also expressed as “A or (B and C) or (D and (B or C)).” The narrow search terms represent core anaphylactic reaction terms whereas Categories B, C and D represent signs and symptoms that are possibly indicative of anaphylactic reaction, with Category B terms representing Upper Airway/Respiratory signs and symptoms, Category C representing Angioedema/Urticaria/Pruritus/Flush signs and symptoms and Category D representing Cardiovascular/Hypertension signs and symptoms. Note that all

PTs within Categories B, C, and D are broad scope terms. The use of the narrow search terms match roughly with Sampson's first tier approach, whereas the broad terms of Categories B, C, and D match roughly with Sampson's second tier approach. Within this second approach using broad terms, it is important to recognize that occurrence of these events should be nearly coincident and develop rapidly after exposure to an antigen; based on recording of events on CRFs, a window wherein the events occur within 2 days of one another (based on the onset dates of the events) is allowed.

The number and percentage of subjects with treatment-emergent anaphylactic reactions will be summarized by treatment group, results for each PT will be provided along with subtotals that first pool narrow and broad terms together, and then, second, for narrow terms only, individual event terms will be ordered by decreasing frequency in the LY3337641 highest dose. A listing will be provided.

6.4.5.8. Gastrointestinal (GI) Perforation, Ulceration, Hemorrhage, or Obstruction

Treatment-emergent AEs potentially related to gastrointestinal (GI) injury will be analyzed using reported AEs. Identification of these events will be based on the PTs of the MedDRA SMQ 20000103, GI perforation, ulceration, hemorrhage or obstruction. A listing of subjects experienced GI perforations, ulcerations, hemorrhage or obstruction will be provided.

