4.5. Benefit/Risk Assessment

There are currently no human data regarding the efficacy of LY3337641 in RA. Nonclinical data and safety data in Phase 1 support further development of LY3337641 in RA at the proposed doses.

The safety profile for LY3337641 has been informed by the results from nonclinical toxicology and safety pharmacology studies and the Phase 1 clinical study (JPDD). The primary toxicity observed in animal studies was gastrointestinal tract injury. Pancreatic and immune system effects were also observed (see Section 5.2.1 of the IB). In humans, the drug was generally well tolerated at dosages up to 40 mg per day. At total daily dosages of 80 mg and higher in the multiple dose portion of the study, significant TEAEs were reported in some subjects. The majority involved skin manifestations, the most common being skin rash. Associated signs and symptoms ranged from pruritus to systemic features such as fever and elevated levels of acute phase reactants. The highest dosage in Study JPDA is 30 mg qd, which is below the doses at which skin rashes or significant TEAEs were reported in Study JPDD. However, adverse events (AEs) of skin rash will be monitored over the course of the study by the medical monitor using blinded data. In addition, skin rash will be monitored by an Assessment Committee using unblinded data. The Assessment Committee members will be independent from the Lilly study team (Section 8.4.7).

More information about the known and expected benefits, risks, serious adverse events (SAEs), and reasonably anticipated AEs of LY3337641 can be found in the IB.

5. Study Population

Part A will include subjects with at least mildly active RA. Part B will include subjects with moderately to severely active RA who have had an inadequate response, loss of response, or intolerance to at least 1 DMARD therapy (synthetic and/or biologic). In Part B only, the percentage of subjects who are naive to biologic DMARDs will be limited to approximately 25% of the study population; the remaining subjects in Part B will have had previous exposure to biologic DMARDs. Subjects participating in Part A will not be eligible to participate in Part B.

Subjects must give written informed consent (approved by Lilly or its designee and the ethical review board [ERB] governing the site) before being allowed to participate in the study and before any screening assessments are performed.

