- parenteral corticosteroids within 28 days prior to baseline or planned treatment during the study. (A single intra-articular corticosteroid injection is permitted within 28 days prior to baseline if no more than 40 mg triamcinolone [or equivalent] is administered and no further injections are planned during the study. The treated joint should be excluded from any joint-specific evaluations during the study.)
- prescription for oral prednisone (or equivalent) >10 mg/day or UNSTABLE PRESCRIBED DOSE within 28 days prior to baseline
- a chronic narcotic drug at an UNSTABLE PRESCRIBED DOSE within 28 days prior to baseline or planned increase/new prescription during the study
- gemfibrozil (a strong cytochrome P450 2C8 inhibitor) or alfentanil, dihydroergotamine, dofetilide, ergotamine, fentanyl, pimozone, or quinidine

(sensitive narrow therapeutic index cytochrome P450 3A substrates) within 28 days prior to baseline or planned treatment during the study

[15] have any clinically significant hematological or chemistry abnormalities at screening, including

- hemoglobin level <8.5 g/dL (<85 g/L)
- total platelet count <100 × 10⁹/L (<100 × 10³/μL or <100 Gi/L)
- total white blood cell count <3.0 × 10⁹/L (<3.0 × 10³/μL or <3.0 Gi/L)
- aspartate aminotransferase (AST) level >2.5 × ULN
- alanine aminotransferase (ALT) level >2.5 × ULN
- creatinine level ≥1.5 mg/dL (≥129 μmol/L)
- amylase >1.5 x ULN
- lipase >1.5 x ULN

A single repeat analysis is allowed according to investigator judgment prior to making a final determination of eligibility. The repeat laboratory test does not require a re-consent because the result does not constitute a screening failure until the clinically significant, out-of-range value is confirmed.

[16] have known hypogammaglobulinemia or a screening serum IgG level <565 mg/dL (<5.65 g/L)

A single repeat analysis is allowed according to investigator judgment prior to making a final determination of eligibility. The repeat laboratory test does not require a re-consent because the result does not constitute a screening failure until the clinically significant out-of-range value is confirmed.

[17] have evidence of or test positive for hepatitis C virus (HCV) at screening (defined as a positive test result for hepatitis C antibody [anti-HCVAb] plus a positive confirmatory test result for HCV [eg, HCV RNA])

Subjects whose results are anti-HCVAb positive and HCV RNA negative can be enrolled in the study, according to investigator judgment.

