- **Outlier/shift displays focusing on low values (where low values are of interest):** A scatterplot, a shift table, and a shift to low table will be created. Unplanned measurements will be included. The scatterplot will plot the minimum value during the baseline period versus the minimum value during the Dosing Period. Lines indicating the reference limits will be included. In cases where limits vary across demographic characteristics, lines indicating the most common limit will be displayed. The shift table will include the number and percentage of subjects within each baseline category (minimum value is low, normal, high, or missing) versus each postbaseline category (minimum value is low, normal, high, or missing) by treatment. Subjects in the safety population will be included in the shift table. The shift from normal/high to low table will include the number and percentage of subjects by treatment whose minimum baseline result is normal or high and whose minimum treatment result is low. Subjects whose minimum baseline result is normal or high and have at least 1 result during the Dosing Period are included. The Fisher's exact test will be used to compare percentages of subjects who shift from normal/high to low between treatments.
- **Outlier/shift displays focusing on high values (where high values are of interest):** The same approach described for low values will be used, except maximum values will replace minimum values.

Alanine aminotransferase (ALT), aspartate aminotransferase (AST), and total bilirubin will not be included in this analysis as different ranges will be used as described in Section 6.4.5.1.

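### SAP 6.4.5.8 and 6.4.3 give no dedicated per-arm summary of GI injury as a group or of marked amylase and lipase rises, although general tables cover both in part

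*SAP*

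**What the plan says.** Protocol 4.5 states: "The primary toxicity observed in animal studies was gastrointestinal tract injury. Pancreatic and immune system effects were also observed". Part B's primary objective (Protocol Table JPDA.2) includes safety and tolerability against placebo.

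For the GI target, SAP 6.4.5.8 defines a group of events: "Identification of these events will be based on the PTs of the MedDRA SMQ 20000103". It says these events will be analyzed, but the one output it names is: "A listing of subjects experienced GI perforations, ulcerations, hemorrhage or obstruction will be provided".

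For the pancreas, Protocol 5.2 criterion [15] excludes subjects with amylase above 1.5 x ULN or "lipase >1.5 x ULN" at screening, and criterion [26] excludes a history of pancreatitis. Both enzymes are in the chemistry panel (Protocol Appendix 3), which is drawn at every dosing-period visit. None of SAP 6.4.5.1 to 6.4.5.8 deals with the pancreas, and the SAP names neither enzyme. As protocol analytes they fall under SAP 6.4.3. For high values that section says: "The same approach described for low values will be used, except maximum values will replace minimum values". The low-value rule thus mirrored restricts the shift-to-low table to subjects whose baseline minimum is normal or high.

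**The concern.** The plan singles out GI injury, defines a query group to capture it, and then produces no rate for that group by arm. Other special topics get more. Anaphylaxis is also identified by a query, and there "The number and percentage of subjects with treatment-emergent anaphylactic reactions will be summarized by treatment group" (SAP 6.4.5.7). Rash has a per-arm count with Fisher's test (SAP 6.4.5.2). Creatinine has graded tables by arm (SAP 6.4.5.5), although the current Protocol 4.5 lists no renal effect.

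For the enzymes, the general shift tables register only the crossing of a laboratory limit. The subjects who start above that limit are the ones the shift-to-high table leaves out.

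At stake is how readily a between-arm difference in the two named animal targets can be seen in a study meant to inform benefit/risk and later trials. No efficacy result is affected.

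**Working it through.** **1. Denominator.** Part B plans 244 subjects in four equal arms: 244 / 4 = 61. The plan's own figure reproduces. With 30% versus 55%, two-sided 0.05 and 80% power, the pooled-variance formula gives

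n = [1.960 x sqrt(2 x 0.425 x 0.575) + 0.8416 x sqrt(0.30 x 0.70 + 0.55 x 0.45)]^2 / 0.25^2 = (1.370 + 0.569)^2 / 0.0625 = 60.2, rounded up to 61.

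Power at 61 per arm is 80.5%. I use 61 only as the safety denominator.

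**2. What the GI group gets, set beside other topics.**

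| Topic | How identified | Per-arm count and % for the topic | Listing |
|---|---|---|---|
| Rash (6.4.5.2) | AE form | Yes, with Fisher's test | Yes |
| Creatinine (6.4.5.5) | CTCAE grade | Yes | Not named |
| Anaphylaxis (6.4.5.7) | MedDRA query | Yes | Yes |
| Hepatic multiples of ULN (6.4.5.1) | Laboratory | Not named | Yes |
| GI injury (6.4.5.8) | MedDRA query | Not named | Yes |
| Pancreas | No subsection | None | None |

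**3. What grouping changes.** The general adverse event tables (SAP 6.4.2) count and test by single preferred term and by system organ class. The event counts here are my assumptions, because the documents give no expected GI rate. For k subjects on one dose and 0 on placebo, the two-sided Fisher p-value is 2 x product over i = 0 to k-1 of (61 - i)/(122 - i).

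| k/61 versus 0/61 | Fisher p |
|---|---|
| 1 (1.6%) | 1.00 |
| 2 (3.3%) | 0.50 |
| 3 (4.9%) | 0.24 |
| 4 (6.6%) | 0.12 |
| 5 (8.2%) | 0.057 |
| 6 (9.8%) | 0.027 |
| 7 (11.5%) | 0.013 |

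Six subjects with six different terms would appear as six rows of 1.6% versus 0%, each p = 1.00. As one group they are 9.8% (exact 95% CI 3.7% to 20.2%) versus 0%, p = 0.027. A term at 1.6% in its arm and absent elsewhere is also below the 5% cut for the common-events table.

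**4. Enzymes under SAP 6.4.3.** I assume amylase and lipase count as analytes for which high values are of interest; the SAP does not say which do.

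- Baseline maximum 1.3 x ULN, on-treatment maximum 8 x ULN: outside the shift-to-high denominator, which needs a normal or low baseline, and recorded as high to high in the full shift table.
- Normal baseline, on-treatment maximum 1.1 x ULN or 8 x ULN: both recorded as normal to high, with no distinction.
- Box plots and the change analysis leave out unplanned measurements. A peak found on an unscheduled draw, which Protocol Appendix 3 permits, is absent from both. The scatterplot does include unplanned values.

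The documents do not say how many subjects enter between 1.0 and 1.5 x ULN, so I cannot size the loss from the denominator.

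**The case against.** A reader might infer that the plan yields no per-arm information on GI injury or pancreatic enzymes at all, or that a difference would go unseen. The documents do not support that.

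- SAP 6.4.2 tests each dose against placebo by system organ class as well as by preferred term. If all six subjects' terms fell in one class and nobody had another event there, the class row would equal the group row, 6/61 versus 0/61. Other GI events would dilute it.
- Serious events and discontinuations due to adverse events are tabulated by arm (SAP 6.4.2.1 and 6.4.2.2), which would capture the gravest cases.
- Protocol 8.4.5 requires clinically significant laboratory findings after the first dose to be reported as adverse events. A large lipase rise should therefore reach the event tables whatever the baseline, subject to the investigator's judgement.
- The scatterplot of baseline against on-treatment maxima, and the box plots with outliers marked, would make an extreme rise visible, though without a count by arm.
- With about 61 subjects per arm, the GI listing can be counted by hand.
- Hepatic multiples of ULN are also only listed, so GI injury is not uniquely neglected. SAP 6.4.5 allows topics to be added.
- Safety p-values are declared descriptive (SAP 6.1 and 6.4). Six versus zero is simply the smallest such count below 0.05, and crossing that line decides nothing.

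All of this stands, and it limits the point to the lack of a dedicated summary. It does not supply a rate for the group that SAP 6.4.5.8 itself defines, or an arm count that separates marked enzyme rises from slight ones.

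**Conclusion.** The point holds as a cheap improvement. Followed as written, the plan names no between-arm rate for the SMQ 20000103 group. Its shift tables cannot register large amylase or lipase rises from a high baseline, or grade rises from a normal one. No data are lost, no bias arises and the primary analysis is untouched.

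The size shown (9.8% versus 0% as a group against six rows of 1.6% versus 0%) rests on assumed counts and an assumed spread over terms. It illustrates the effect of grouping and predicts nothing. The enzyme point rests on the text alone and has no size, because baseline enzyme levels are not given.

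**What to change.** In SAP 6.4.5.8, add the number and percentage of subjects in each arm with at least one treatment-emergent term from SMQ 20000103, and keep the listing. A descriptive Fisher test, as for rash, is optional.

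Add a table by arm of maximum postbaseline amylase and lipase in prespecified multiples of ULN. It should include every subject with a postbaseline value, whatever the baseline, and use unplanned as well as planned measurements. The sponsor should fix the cut-points before Part B results are unblinded, so that they are not chosen after seeing the data. A grouped count of pancreatitis events is optional.

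The cost is one or two more descriptive safety tables from data already collected, with no new visits, samples or subjects.

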6.5. Other Analyses

6.5.1. Subgroup Analyses

For Part B, subgroup analyses will be conducted on the mITT population at Week 12 for response rates in ACR20, ACR50, ACR70, DAS28-hsCRP <2.6, DAS28-hsCRP \leq 3.2, and HAQ-DI Improvement \geq 0.22; and for change from baseline in HAQ-DI and DAS28-hsCRP. The results of subgroup analyses will be also presented in forest plots as deemed necessary.

The following subgroups (but not limited to only these) will be categorized into disease-related characteristics and demographic characteristics, and will be evaluated:

- Sex: (male, female)
- Age group: (18 to \leq median > median to 65)
- Region (Part A: North America-US; South America - Mexico; Europe-Austria, Italy, Slovakia, and Poland)
(Part B: North America-US; South America – Mexico, Argentina; Europe – Austria, Italy, Slovakia, Poland, Spain, Germany; Others – Korea, Japan, South Africa, Australia)
- Previous RA therapy (biologic DMARD (Yes/No))
- Used steroid concomitantly in treatment period (Yes/No)
- Baseline DAS28-hsCRP (\leq 5.1, >5.1)
- Duration of RA from diagnosis date (\leq 5 years, >5 years)

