6.8. Concomitant Therapy

Allowed and excluded medications and procedures will be provided in the Listing of Excluded and Restricted Medications tool.

Subjects on concurrent, protocol-permitted RA treatments should remain on stable doses during the course of the study.

Subjects taking other concomitant medications should be on stable doses at baseline and should remain at stable doses throughout the study to the extent possible, unless changes are needed for

treatment of an AE. The introduction of any other new prescription or over-the-counter drugs is to be avoided during the study unless required to treat an AE. Any medication used during the course of the study must be documented.

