7.1.4. Permanent Discontinuation from the Study

Possible reasons that may lead to permanent discontinuation include

- enrollment in any other clinical trial involving an IP or enrollment in any other type of medical research judged not to be scientifically or medically compatible with this study
- participation in the study needs to be stopped for medical, safety, regulatory, or other reasons consistent with applicable laws, regulations, and good clinical practice (GCP)
- investigator decision
 - the investigator decides that the subject should be discontinued from the study drug or study
 - the subject, for any reason, requires treatment with another therapeutic agent that has been demonstrated to be effective for treatment of RA but is contraindicated in this study (in such cases, discontinuation from the study occurs prior to introduction of the new agent)
- subject decision
 - the subject requests to be withdrawn from the study

The reason for and date of discontinuation from study will be collected for all randomized subjects. All subjects who have received study drug and discontinue the study early will have end-of-study procedures performed as shown for the EDV in the Schedule of Activities ([Appendix 2](#)). Subjects who are randomized but discontinue the study prior to receiving a single dose of study drug will not have an EDV or a safety follow-up visit.

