9.7.2. Subgroup Analyses

Subgroup analyses will be conducted for ACR20, ACR50, ACR70, and DAS28-hsCRP using the modified intent-to-treat population using Part B data. Subgroups that may be evaluated include

past or ongoing RA treatment at baseline and baseline DAS28-hsCRP. Details will be provided in the SAP.

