6.2.4. Previous and Concomitant Therapy

Previous therapy is defined as therapy for the primary disease that has been discontinued prior to screening, and concomitant therapy is defined as therapy that is ongoing during the study.

Previous therapy will be collected at screening. Concomitant therapy will be collected at each visit. The reported term will be classified by the WHO drug dictionary and summarized using number and frequency by WHO drug ATC classification and treatment group.

Previous and concomitant therapies for the primary disease collected at screening will be summarized by:

- Types and number of therapies (NSAIDs, corticosteroid, cDMARDs, biologic agents)
- Average daily dose of corticosteroid
- Average weekly dose of methotrexate
- Number and type of cDMARDs (methotrexate only, methotrexate + other cDMARD(s), non-methotrexate only)
- Number of previous biologic agents (0, 1, 2, ≥ 3), name of previous biologic agents, and type of biologic agents (anti-TNF, no anti-TNF).

Concomitant therapies, defined as therapies with a stop date on or after the date of the first dose of the study drug, used for the primary disease will be summarized as below:

- Types and number of therapies (NSAIDs, corticosteroid, cDMARDs)
- Average daily dose of corticosteroid
- Average weekly dose of methotrexate
- Number and type of cDMARDs (methotrexate only, methotrexate + other cDMARD(s), non-methotrexate only).

Concomitant therapies used for conditions other than the primary disease during the Dosing Period will also be summarized. New initiated concomitant therapies after the last study drug in the study follow-up period, defined as therapies with a start date on or after the stop date of the study drug, will be summarized.

The ATC code H02 will be used to select all possible corticosteroids (H02 Corticosteroids for systemic use with route of Oral). All unique preferred terms in the database falling under the ATC code in [Appendix 1](#) will be reviewed by the medical group in order to determine which ones should be included. All corticosteroid doses need to be converted to prednisone equivalent doses. If additional conversion factors are required, these will be added prior to database lock.

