6.5.5. Analyses for the Optional Long-Term Extension Period

The objective of the optional long-term extension period is to collect long-term safety and efficacy data on LY3337641. For all subjects entering the long-term extension, the baseline visit is defined as Visit 106 in Part B.

Subjects will be grouped according to the treatment group in long-term extension and randomized treatment in Part B:

LY5mg(LTE)_Placebo(Part B); LY5mg(LTE)_LY5mg(Part B);

LY10mg(LTE)_Placebo(Part B); LY10mg(LTE)_LY10mg(Part B);
LY30mg(LTE)_Placebo(Part B); LY30mg(LTE)_LY30(Part B)

Unless otherwise specified, efficacy and health outcomes analyses will be conducted on the mITT population, defined as all randomized subjects receiving at least 1 dose of study drug. The analysis population (for applicable treatment outcome measures) will be all subjects with both a baseline and at least 1 postbaseline data measurement.

All variables and the change from baseline will be summarized by descriptive statistics. The statistics for continuous variables include mean, median, standard deviation, and number of observations. Categorical variables will be summarized by counts and percentages. No statistical hypothesis testing will be performed. The efficacy and health outcomes will be summarized as described in Section 6.3.

Safety analysis will be performed for all subjects entering the LTE, receiving at least 1 dose of the study drug and who do not discontinue the study for the reason “Lost to Follow-up” at the first postbaseline visit in LTE. The safety analysis will be conducted as described in Section 6.4. Duration of exposure will be calculated for each subject entering the LTE and summarized by treatment group for LTE period and cumulatively from Part B. Subjects who do not achieve response to study drug are eligible for rescue therapy at Week 16 and Week 20. From Week 24 onward, rescue therapy may be implemented for any subject determined to have ongoing active disease as assessed by the investigator. The safety, efficacy, and health outcome measures will be summarized separately for subjects who receive rescue therapies as described in Section 6.3 and Section 6.4.

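### The Part B steroid subgroup is defined by use during treatment, so comparisons of arms within it are not protected by randomisation

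*SAP*

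**What the plan says.** SAP 6.5.1 plans Week 12 subgroup analyses in the Part B mITT population. The outcomes are ACR20/50/70, remission and low disease activity by DAS28-hsCRP, a HAQ-DI improvement threshold, and change in HAQ-DI and DAS28-hsCRP. One of the seven listed factors is "Used steroid concomitantly in treatment period (Yes/No". The list is open-ended, and forest plots are optional.

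SAP 6.2.4 gives two descriptions of concomitant therapy. The general one is therapy that continues during the study. The specific one, attached to treatments for RA, reads "Concomitant therapies, defined as therapies with a stop date on or after the date of the first dose of the study drug". Neither puts a condition on the start date.

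Protocol 9.7.2 says the subgroups that may be examined include "past or ongoing RA treatment at baseline and baseline DAS28-hsCRP", and leaves details to the SAP.

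Four provisions limit new steroid use during dosing:

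- Protocol 6.8 asks for stable doses of permitted RA treatments, and says that introducing other new prescription or non-prescription "drugs is to be avoided during the study unless required to treat an AE".
- Protocol 5.2, criterion [14], excludes a "prescription for oral prednisone (or equivalent) >10 mg/day or UNSTABLE PRESCRIBED DOSE within 28 days prior to baseline". Unlike the parenteral steroid item in the same criterion, it does not mention treatment planned during the study.
- Protocol 7.1.4 covers a subject who needs an effective RA agent that the study does not permit: "discontinuation from the study occurs prior to introduction of the new agent".
- Rescue is described only for the extension, where subjects without a response are "eligible for rescue therapy at Week 16 and Week 20" (SAP 6.5.5).

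**The concern.** A subgroup comparison of randomised arms is unbiased only if treatment cannot change who belongs to the subgroup. A subject who is off steroids at baseline and starts one in, say, Week 6 is counted as Yes. If the start follows an adverse event of the study drug, or goes with poor response, the Yes group gains subjects selected by treatment and outcome, and the No group loses them.

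The route is plausible here because skin rash is the adverse event of special interest. Protocol 8.4.6 allows drug treatment of a rash and also allows study drug to continue or be restarted. The documents do not name steroids in that setting; that one could be given is an inference. A starter who later stops study drug permanently is also a nonresponder by rule (SAP 6.1.3.1).

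What is at stake is one display. The Yes and No estimates could differ for reasons unrelated to effect modification, yet stand beside six factors that do not have this problem.

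**Working it through.** **1. When each listed factor is fixed**

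| Factor (SAP 6.5.1) | Can treatment change it? |
|---|---|
| Sex, age group, region | No |
| Previous biologic DMARD | No |
| Baseline DAS28-hsCRP | No |
| RA duration from diagnosis | No (end date not stated) |
| Steroid use in the treatment period | Yes |

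One of the seven listed factors is measured after randomisation.

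**2. The plan's own figures.** Protocol 9.1 and SAP 5.2 assume 30% ACR20 on placebo, a 25-point difference, two-sided 0.05 and 61 per arm for at least 80% power. The pooled-variance formula gives

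n = [1.96·√(2·0.425·0.575) + 0.8416·√(0.30·0.70 + 0.55·0.45)]² / 0.25² = 60.2, rounded up to 61,

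with 80.5% power at 61. These rates are used below.

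**3. Spurious subgroup difference.** The documents give neither the share of baseline steroid users nor a start rate, so both are assumptions. Let b be the share of baseline users, s the share of baseline non-users who start, and p the arm's response rate, taken as equal in users and non-users. Suppose every starter is a nonresponder. Then

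- No rate = p / (1 − s)
- Yes rate = b·p / [b + (1 − b)·s]

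The true effect is 25 points in both groups, so any Yes/No difference in effect is spurious.

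Starts in the active arm only, b = 0.4, placebo 30% in both groups:

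| s | Active No | Active Yes | Spurious difference |
|---|---|---|---|
| 2% | 0.55/0.98 = 56.1% | 0.22/0.412 = 53.4% | 2.7 points |
| 5% | 0.55/0.95 = 57.9% | 0.22/0.43 = 51.2% | 6.7 points |
| 10% | 0.55/0.90 = 61.1% | 0.22/0.46 = 47.8% | 13.3 points |

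The last row means 0.6 × 0.10 = 6% of the arm, or 3.7 of 61 subjects.

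Other assumptions:

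- Equal starts in both arms, b = 0.4, s = 2%: placebo No 30.6%, Yes 29.1%; effects 25.5 and 24.3; difference 1.2 points. At 5% it is 3.1 and at 10% it is 6.0.
- Active-arm starts at 2%, 5% and 10%: with b = 0.2, 5.2, 12.1 and 21.8 points; with b = 0.6, 1.8, 4.7 and 9.5 points.

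**4. A second parameterisation.** Now let a share s′ of non-responding non-users start. Then Yes rate = b·p / [b + (1 − b)(1 − p)·s′] and No rate = p / [1 − (1 − p)·s′]. Take b from 0.3 to 0.5 and s′ from 2% to 20%.

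- No drug effect (30% in both arms), starts in one arm only: a false arm difference of 0.4 to 7.4 points in Yes and 0.4 to 4.9 points, with opposite sign, in No. With equal starts it is zero.
- 30% and 55%, equal s′ in both arms: the largest case is b = 0.3, s′ = 20%. Yes shows 45.45 − 22.61 = 22.84 points and No shows 60.44 − 34.88 = 25.56 points, a difference of 2.7 points.

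**5. Against sampling error.** For b = 0.4, s = 10%, active-arm starts, the expected cells are active No 32.9, active Yes 28.1, placebo No 36.6, placebo Yes 24.4:

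SE = √(0.611·0.389/32.9 + 0.478·0.522/28.1 + 0.21/36.6 + 0.21/24.4) = 17.5 points.

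The 13.3-point case is 13.3/17.5 = 0.8 SE.

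**The case against.** The strongest reply is that the route into Yes is nearly closed. The stop-date definition in SAP 6.2.4 belongs to treatments for RA, so a steroid given for a rash might not count, while a new steroid for RA would run against the stable-dose instruction. SAP 6.2.4 and Appendix 1 select corticosteroids by ATC code H02 and oral route, which removes topical and injected products. If few subjects change group, the two definitions give almost the same display.

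Much of this stands. It is why the low end of the range is more likely. It does not close the route: the item refers to the treatment period without limiting indication, the general definition in SAP 6.2.4 covers any therapy continuing during the study, and new oral steroids are not expressly barred. SAP 6.5.1 does not say which rule governs the item. Excluded concomitant medication removes a subject from the per-protocol set (Table JPDA.6.1), not from the mITT set used here.

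Two further objections are accepted. Protocol 9.7.2 is permissive, so the SAP breaches nothing; it only moves, without giving a reason, from the protocol's baseline example to an on-treatment window. The direction of bias is also unknown: if starters respond more often than others, the sign reverses.

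**Conclusion.** The concern holds. As written, this is the only listed subgroup factor that treatment can influence, and randomisation does not protect the arm comparison within its levels.

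The size cannot be derived from the documents. It is zero if nobody starts a steroid or if starters respond like everyone else. It is about 1 to 3 points at a 2% start rate with 40% baseline users, and reaches 13.3 points only if 10% of active-arm baseline non-users start, none in placebo do, and all starters fail to respond. A smaller baseline share makes it larger.

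The consequence is a possibly biased point estimate in one subgroup display. The primary ACR20 analysis, the significance level and the sample size are unaffected, and SAP 6.5.1 attaches no interaction test or decision rule. This should be changed because a sound alternative is available at almost no cost; it does not threaten the trial's main conclusion.

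**What to change.** In SAP 6.5.1, replace the item with systemic corticosteroid use at baseline (Yes/No), defined as therapy ongoing at the first dose of study drug. State whether the ATC H02 oral rule of Appendix 1 applies and which indications count. Report steroid starts or increases after baseline only in a descriptive table by arm.

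The cost is about one line of SAP text plus that table. No new data are needed: SAP 6.2.4 already states that "Previous and concomitant therapies for the primary disease collected at screening will be summarized by" categories that include corticosteroids and their average daily dose. Because stable dosing is requested, few subjects should change group. With a baseline definition, the spurious difference between arms within the subgroup is zero in expectation, and 61 per arm stands.
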